## **1. Abstract**

The dermatologic Surgery Unit at the University of Missouri Department of Dermatology does over 2000 procedures annually on an outpatient basis under local anesthesia with patients completely awake for their procedures. Most of these procedures are on the head and neck, and as such, electrosurgical smoke is produced near the nose and mouth of the patients with no means for minimizing that exposure because, as yet, there is no institutional policy on surgical smoke evacuation. It has been our experience that patients uniformly find the odor of the smoke offensive, with a few patients experiencing wartime PTSD episodes due to the smell. It has recently been highlighted in the medical literature that there are health risks for medical providers and staff related to inhalation of electrosurgical smoke. We seek to define patient attitudes toward the use of smoke evacuation and the potential impact of an outpatient smoke evacuation protocol on patient satisfaction.

## **2. Objectives**

Perform a randomized controlled trial to prospectively determine the effect of smoke evacuation on the patient experience by studying:

1. The degree to which patients notice surgical smoke
2. The effect that smoke evacuation has on patient satisfaction with their procedure
3. The relative value of smoke evacuation to the patient

## **3. Background**

During surgery, use of electrosurgical units causes thermal destruction of tissue and generates smoke that has been shown to contain harmful chemicals as well as live cellular material. A study has shown that treating one gram of tissue with an electrosurgical unit produces chemical byproducts equivalent to smoking six unfiltered cigarettes. Electrosurgical smoke has been shown to include nitriles, benzenes, carbon monoxide, hydrogen cyanide, indoles, phenols, pyridine, pyrrole, styrene, toluene, and xylene. Benzene is a known trigger for leukemia. Surgical smoke exposure has been shown to cause pathologic lung changes in rats including interstitial pneumonia, bronchiolitis, and emphysema in a dose-dependent manner. Exposure to surgical smoke in humans has also been linked to illness and symptoms including acute and chronic inflammatory changes of the lungs, anemia, eye irritation, hypoxia, dizziness, nasopharyngeal lesions, vomiting, sneezing, throat irritation, and weakness. Because blood particles, viruses, and bacteria can travel via smoke it may transmit diseases such as human papilloma virus (HPV) which have been recovered from plume samples. HIV DNA has also been identified in surgical smoke with transmission to cultured cells. In one study, smoke specimens taken from thirteen procedures grew coagulase-negative *Staphylococcus*, *Corynebacterium*, and *Neisseria* species. Citing these known health risks and our experience of patients almost uniformly objecting to the smell and presence of the smoke during their procedures, we seek to define patient attitudes

toward smoke evacuation as this information will be useful in forming hospital policy and possibly national policies on the value of smoke evacuation.

#### **4. Study Procedures**

- a. Study design:
  - i. Randomized Controlled Trial
  - ii. Patients: All adult (> 18 years old) patients presenting for Mohs surgery and reconstruction for the treatment of nonmelanoma skin cancer on the head and neck
  - iii. To avoid response bias, patients will be asked to participate in a research study that determines the impact of external sensory stimuli (lights, smoke, and noise) on their preferences during outpatient surgery. Patients will not be made aware of the smoke evacuation randomization component of study until debriefing following questionnaire completion.
  - iv. After obtaining informed consent, patients will be randomized into two arms, a treatment arm where patients will have smoke evacuation used during the entirety of their procedure and a control arm where patients will have surgery carried out with standard electrosurgery without smoke evacuation. The control arm represents the current standard of care for patients receiving this type of procedure both inside our institution and nationwide.
  - v. Immediately following surgery and prior to departure from their clinical visit, patients will be asked to respond to a questionnaire. To prevent response bias patients will be asked questions about their experience with surgical lights, surgical smoke, and surgical noises during their procedure. Questionnaires have no identifiers and subjects will deposit completed forms into a collection box to maintain anonymity.
  - vi. After completing the questionnaire, patients will be debriefed to explain deception involved in smoke evacuation randomization and asking questions about light, noise, and smoke when goal of the study is only to determine patients experience with smoke.
- b. Study duration and number of study visits required of research participants.
  - i. Duration sufficient to enroll approximately 160 patients (80 per treatment arm). No additional patient visits will be required beyond the visit normally required for their procedure.
- c. Blinding, including justification for blinding or not blinding the trial, if applicable.
  - i. N/A.
- d. Justification of why participants will not receive routine care or will have current therapy stopped.
  - i. Care will be identical in both arms except for the introduction of smoke evacuation in the treatment arm. Smoke evacuation is not our institutional policy presently and is not the nationwide norm.
- e. Justification for inclusion of a placebo or non-treatment group.
  - i. As stated, the “non-treatment” group is still being cared for in accordance with the current nationwide standard of care.
- f. Definition of treatment failure or participant removal criteria.
  - i. We do not foresee a scenario where treatment failure would be possible as this research is targeting the effect on patient experience of an intervention with a tool in our operating suite. A patient would be removed from the study if they did not complete their procedure. This is an exceedingly rare occurrence.
- g. Description of what happens to participants receiving therapy when study ends or if a participant’s participation in the study ends prematurely.

- i. There would be no effect on the patient.

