## **7. Study Statistics**

- a. Primary outcome variable.
  - i. Degree to which patient notices surgical smoke
  - ii. Degree to which surgical smoke affected patient satisfaction
  - iii. Perceived value of smoke evacuation for the patient
- b. Secondary outcome variables.
  - i. None
- c. Statistical plan including sample size justification and interim data analysis.
  - i. Results of a completed pilot study were used to determine a sample size of 140-150 is necessary to test with a 0.05 significance level and greater than 90% power to reject the null hypothesis.
  - ii. All of the responses to the questions will be on an ordinal scale. Outcomes will be compared using the Cochran-Armitage test for trend.
- d. Early stopping rules.
  - i. None.

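### Does the anonymous questionnaire leave no way to tell which randomised arm a response came from?

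*Combined protocol and SAP*

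**What the plan says.** Section 4.a.iv randomises patients to two arms. One is "a treatment arm where patients will have smoke evacuation used during the entirety of their procedure"; the other has standard electrosurgery without evacuation. Section 4.a.iii keeps patients uninformed: "Patients will not be made aware of the smoke evacuation randomization component of study until debriefing following questionnaire completion". Section 4.a.v has them answer a questionnaire before they leave the clinic and adds: "Questionnaires have no identifiers and subjects will deposit completed forms into a collection box to maintain anonymity".

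Section 7.a lists three primary outcomes, and 7.b lists no secondary ones. On analysis, 7.c.ii states "All of the responses to the questions will be on an ordinal scale" and "Outcomes will be compared using the Cochran-Armitage test for trend". That the primary outcomes come from this questionnaire is an inference from these sentences, but a safe one, since no other data source is described.

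On numbers, 4.b.i plans about 160 patients, 80 in each arm, and 7.c.i says that "a sample size of 140-150 is necessary to test with a 0.05 significance level and greater than 90% power". The only removal rule, in 4.f.i, is "A patient would be removed from the study if they did not complete their procedure", which the protocol expects to be very rare. Section 4.c.i marks blinding as not applicable.

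No section mentions an arm code, a form version, separate boxes or a study number.

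**The concern.** The Cochran-Armitage test relates an ordered scale to a two-level variable, here the randomised arm. If a form carries nothing that shows its arm, it cannot enter the comparison. Patients cannot supply the arm themselves, because they do not learn of the randomisation until the form is complete. An unnumbered form cannot be traced once it is in the box, so a missing or wrong label cannot be put right later. Staff who followed 4.a.v to the letter might hand the same unmarked sheet to everyone.

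A second question follows from the first. The treatment arm is described as evacuation for the whole procedure, and a patient whose evacuation was interrupted is not removed under 4.f.i. A reader may therefore ask whether that form should be labelled by allocation or by what was used.

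At stake would be all three primary outcomes.

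**Working it through.** **1. The plan's own sample size.** Section 7.c.i gives 140-150 for a 0.05 level and more than 90% power. It cannot be reproduced, because the pilot results are not given. It can only be solved backwards for a standardised difference d, assuming a two-sided test and a normal approximation, with n per arm:

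d = (1.960 + 1.282) × √(2/n)

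- n = 70 (N = 140): 3.242 × 0.1690 = 0.548
- n = 75 (N = 150): 3.242 × 0.1633 = 0.529

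With every form correctly labelled and 160 forms analysed (n = 80, √(2/80) = 0.1581), power is Φ(0.548/0.1581 − 1.960) = 93.4% or Φ(0.529/0.1581 − 1.960) = 91.7%. The stated target is then met.

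**2. What a faulty label would cost.** Suppose a share m of forms, equal in both arms, is credited to the wrong arm. The difference shrinks to d(1 − 2m), and at N = 140 or 150 power is about Φ(3.242 × (1 − 2m) − 1.960), ignoring the far tail:

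| m (assumed) | Power |
|---|---|
| 2% | 87.5% |
| 5% | 83.1% |
| 10% | 73.7% |
| 50% (no label at all; both tails counted) | 5.0% |

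The last row is why the matter looks grave. But every m here is an assumption. The documents give no mislabelling rate and no reason to expect one. Using m = 50% treats a step that is not described as a step that will not be done.

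**3. Does the text rule out a label?** Set side by side:

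- 4.a.v gives its own purpose, anonymity. That bars marks that point to a person. A mark shared by about 80 patients does not.
- 4.a.iii requires that patients do not learn of the randomisation. A discreet code, or two form versions that look alike to a patient, respects this.
- 4.c.i plans no blinding, so staff who know the allocation can issue the right form or direct it to the right box.
- 4.a.iv defines the arms by randomisation. The natural label is therefore the allocated arm, including for a patient whose evacuation was interrupted.

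No two of these statements conflict, and none conflicts with the test in 7.c.ii.

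**4. Margin for forms that cannot be used.**

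- 160 − 150 = 10 forms; 10/160 = 6.25%; 80 − 75 = 5 per arm if losses are even
- 160 − 140 = 20 forms; 20/160 = 12.5%; 80 − 70 = 10 per arm if losses are even

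Unreturned forms, unreadable labels and removals under 4.f.i all draw on this margin. One form is 1/80 = 1.25% of an arm.

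**5. Can losses be compared between arms?** Yes, once forms show their arm. The number randomised to each arm is known from the allocation, so loss per arm is the number randomised minus the readable labelled forms received. A count of forms issued would only divide that loss by cause.

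**The case for a change.** The strongest case for acting is that the step is both essential and irreversible. Every primary outcome depends on it, the protocol already describes how the forms are handled, and one sentence there would cost almost nothing. It would also settle whether the label follows allocation or use. Even a form that already carries a code would lose nothing by having the practice recorded.

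Part of this stands. The protocol is silent, and an unmarked form could not be assigned later. The rest does not carry the point further. Silence about the layout of a form that is not among the documents is no evidence that the layout is deficient. A printed code is only one possible link; form versions or separate boxes would do as well, and nothing excludes them. Interrupted evacuation is a hypothetical for which the documents give no frequency, and randomisation already defines the arms. Individually linked numbers would allow a form to be retrieved if a patient withdrew after debriefing, but they would weaken the anonymity that 4.a.v deliberately chose. That is a fair trade-off for the investigators to make.

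**Conclusion.** The concern does not call for a change. The protocol leaves out a routine handling step that investigators comparing two randomised arms will fill in the obvious way, by marking forms with the allocated arm in a manner patients cannot recognise. Writing it down would be an optional clarification; no stated rule produces a wrong analysis.

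If forms are marked in this way, the effect on the results is nil. The only size the documents support is the margin of 10-20 forms (6.25-12.5% of 160) between enrolment and the stated need, and that margin favours the plan. The power figures for mislabelled forms rest on assumed rates and a back-solved effect, and they do not describe anything the protocol sets out.

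The conclusion rests on two assumptions: that the ban on identifiers means personal identifiers, which the stated purpose of anonymity supports, and that staff know the allocation when they hand out the form, which fits a plan without blinding. If the first were wrong and truly identical forms went into a single box, the between-arm comparison would fail, but nothing in the documents indicates that this is intended.

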## **5. Inclusion/Exclusion Criteria**

- a. Adult (18 years old and older) patients being treated for nonmelanoma skin cancer on the head and neck with Mohs surgery and a subsequent repair will be included in this study

## **6. Drugs/ Substances/ Devices**

- a. The smoke evacuation device being used does not make contact with patients or pose any additional risk to study patients. There is evidence to suggest that use of smoke evacuation may decrease risk to patients during surgical procedures by eliminating hazardous smoke.

## **7. Study Statistics**

- a. Primary outcome variable.
  - i. Degree to which patient notices surgical smoke
  - ii. Degree to which surgical smoke affected patient satisfaction
  - iii. Perceived value of smoke evacuation for the patient
- b. Secondary outcome variables.
  - i. None
- c. Statistical plan including sample size justification and interim data analysis.
  - i. Results of a completed pilot study were used to determine a sample size of 140-150 is necessary to test with a 0.05 significance level and greater than 90% power to reject the null hypothesis.
  - ii. All of the responses to the questions will be on an ordinal scale. Outcomes will be compared using the Cochran-Armitage test for trend.
- d. Early stopping rules.
  - i. None.

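### Three unranked primary outcomes share one 0.05 level, with no rule for what counts as a positive result or how multiple tests are handled

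*Combined protocol and SAP*

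**What the plan says.** Section 7.a of the combined protocol and SAP lists three primary outcomes:

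- "Degree to which patient notices surgical smoke"
- "Degree to which surgical smoke affected patient satisfaction"
- "Perceived value of smoke evacuation for the patient"

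Section 7.b lists no secondary outcomes. Section 2 gives three matching objectives, the last being "The relative value of smoke evacuation to the patient", and does not rank them either.

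Section 7.c.i states that "a sample size of 140-150 is necessary to test with a 0.05 significance level and greater than 90% power to reject the null hypothesis". The null hypothesis is singular and is not linked to an outcome. Section 7.c.ii adds "All of the responses to the questions will be on an ordinal scale" and "Outcomes will be compared using the Cochran-Armitage test for trend". It gives no significance level of its own and does not say how many questions feed each outcome.

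No section gives an order of testing, a division of the 0.05, or a statement of whether one, all or each of the three outcomes decides the result. Planned enrolment in section 4.b.i is about 160, 80 per arm.

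**The concern.** With three primary outcomes and one significance level, the meaning of 0.05 depends on how the results are turned into a claim, and the plan leaves that open. If one significant outcome out of three is enough to report a primary finding, the trial has up to three chances of a false claim and its overall error can exceed 5%. The power statement has a similar gap: a reader cannot tell whether the figure above 90% applies to one outcome, to each, or to all three together.

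Section 9 intends the results to inform policy at the institution and possibly nationally. If one or two outcomes turn out significant, whether that is success, partial success or failure would be decided after the data are known.

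**Working it through.** **The plan's own figure.** The 140-150 cannot be reproduced: the documents give no effect size, response distribution, sidedness or named outcome, only a reference to a pilot study. Working backwards with a two-sample normal formula (two-sided 0.05, 90% power), the standardised difference is (1.960 + 1.2816) × √(4/N), which is 0.55 at N = 140 and 0.53 at N = 150. That is plausible but is not a check.

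**Inputs from the documents.** Three primary outcomes (7.a); level 0.05, power above 90%, N 140-150 (7.c.i); about 160 enrolled (4.b.i).

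**Assumptions.** Each outcome is tested once at two-sided 0.05, the only level given. Test statistics are normal with a common correlation ρ. The outcomes come from one questionnaire (4.a.v), so some correlation is likely; its size is not documented, and 0 to 0.9 is used as a range.

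**Chance of at least one false claim when any significant outcome counts.** Let m be the number of outcomes with no true effect and c = 1.960. For ρ = 0 the chance is 1 − 0.95^m:

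- m = 3: 1 − 0.95³ = 0.1426
- m = 2: 1 − 0.95² = 0.0975
- m = 1: 0.05

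For ρ > 0 it is 1 − ∫ φ(t) [Φ((c − √ρ t)/√(1−ρ)) − Φ((−c − √ρ t)/√(1−ρ))]^m dt.

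| Real effects | ρ = 0 | ρ = 0.5 | ρ = 0.9 |
|---|---|---|---|
| None (m = 3) | 14.3% | 12.5% | 8.4% |
| One (m = 2) | 9.8% | 9.1% | 7.0% |
| Two (m = 1) | 5.0% | 5.0% | 5.0% |

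Simulated five-level ordinal responses, 80 per arm with a trend test and latent correlation 0 / 0.5 / 0.9, gave 14.2 / 13.4 / 9.0% with no effect and 9.7 / 9.6 / 7.4% with one. One-sided testing at ρ = 0.9 gives 8.0% and 6.8%.

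**If all three must be significant.** The false-claim rate is at most 5%. If per-outcome power is exactly 90% at 140-150, joint power there is 0.90³ = 73% at ρ = 0 and 85% at ρ = 0.9. With 160 analysed it is 77-90%. Starting from 95% per outcome, it is 89-95% with 160. A shortfall below 90% is therefore possible but not established, because the plan says greater than 90%.

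**Holm at an overall 0.05.** The chance of a false claim is 4.9% (ρ = 0) to 3.0% (ρ = 0.9) with no effect, and 4.8% to 3.0% with one.

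**Power cost of Holm.** In the worst case an outcome must pass the first step, 0.05/3, for which z = 2.394.

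- From 90% at 140-150, noncentrality is 1.960 + 1.2816 = 3.2415. With 140-150 analysed: Φ(3.2415 − 2.394) = 80%.
- With 160 analysed: Φ(3.2415 × √(160/150) − 2.394) = 83%, and with √(160/140), 86%.
- From 95%, the same steps give 89% with 140-150 and 91-93% with 160.

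If all three outcomes have equal effects, average per-outcome power under Holm with 160 analysed is 87-92% (from 90%) or 93-97% (from 95%).

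**The case against.** The strongest reply is that the plan never says any single significant outcome makes the trial positive. Sections 2 and 9 describe three distinct questions (noticing, satisfaction and value), and nothing combines them into one claim. Read that way, each question has its own 5% error, and whether to adjust is a matter of choice. This stands as far as it goes: the inflation belongs to one of three possible readings. But the plan does not adopt the separate-claims reading, and a single 0.05 would then not describe the trial as a whole.

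A reader might infer that the trial's false-positive rate is simply 14%. The documents do not support that. The figure needs the any-one reading, no real effect on any outcome, and uncorrelated outcomes.

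A reader might also take the abstract's remark, "It has been our experience that patients uniformly find the odor of the smoke offensive", to mean that exactly one real effect is the case to plan for. An offensive smell bears on satisfaction as much as on noticing, and the Background section likewise reports near-universal objection to the smoke. On the sponsor's own premise, two real effects are at least as plausible as one, and then there is no inflation.

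It is also fair that all three outcomes are prespecified, that there is no lower tier from which one could be promoted, and that a reader could apply Holm to three reported p-values. This limits the harm. It does not replace a stated rule, and it does not say what the power refers to.

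Finally, the extra 10-20 patients may be an allowance for losses, since section 4.f removes those who do not complete the procedure. The cost of any adjustment should therefore be judged at 140-150 as well as at 160.

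**Conclusion.** The omission is established by the text: three unranked primary outcomes, one level, one power figure for an unnamed hypothesis, one test, and no success or multiplicity rule. Confidence in this is high.

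The consequence is conditional. Overall error exceeds 5% only if any significant outcome is reported as a primary finding and fewer than two effects are real. Confidence in its size is moderate, because correlation, sidedness and the number of tests per outcome are undocumented. More than one test per outcome would raise the error.

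The documents do not show that the trial is underpowered or that 140-150 is wrong. They show that the 0.05 and the figure above 90% cannot be tied to a defined claim. The gap is worth closing because it concerns the primary analysis and costs only wording.

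**What to change.** Before any outcome data are seen:

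1. In 7.c.ii, state that the three primary outcomes are tested with Holm's procedure at an overall two-sided 0.05. Alternatively, state a fixed sequence in an order the sponsor chooses, each outcome tested at two-sided 0.05 only if the previous one is significant.
2. In 7.c.i, name the outcome or outcomes to which the power above 90% refers, and restate it under the chosen rule.

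Neither option needs extra patients, but both have a price. Holm needs no ranking and lowers per-outcome power as shown above, so the figure above 90% may have to be restated lower. Holding 90% per outcome even in the worst case would take about 1.29 times the sample, or 180-193 instead of 140-150; this is not required for the fix.

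A fixed sequence keeps the full 0.05 for the first outcome (92-93% power with 160 analysed, if it was exactly 90% at 140-150). It obliges the sponsor to rank objectives that section 2 leaves unranked, and later outcomes cannot be confirmatory once an earlier one fails. With equal effects and 160 analysed, the second outcome is reached and passed with probability 84-91%, the third with 77-90%.

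### Tumour site, a plausible influence on noticing smoke, is used in neither allocation nor analysis: a cheap efficiency gain forgone, not an error in the plan

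*Combined protocol and SAP*

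**What the plan says.** - **Allocation** (section 4.a.iv): "After obtaining informed consent, patients will be randomized into two arms". No stratification factor, blocking or sequence method is described.
- **Analysis** (section 7.c.ii): the responses are ordinal and "Outcomes will be compared using the Cochran-Armitage test for trend". No stratum or covariate is named, and the number of response levels is not given.
- **Rationale** (section 1): most procedures are on the head and neck, so that "electrosurgical smoke is produced near the nose and mouth of the patients".
- **Eligibility** (sections 4.a.ii and 5.a): Mohs surgery with repair for nonmelanoma skin cancer at any head and neck site.
- **Data collection** (section 4.a.v): the questionnaires cannot be traced to a patient and are dropped in a collection box. The documents do not say whether the form shows the arm or the tumour site.
- **Size** (sections 7.c.i and 4.b.i): "a sample size of 140-150 is necessary" for a 0.05 level and "greater than 90% power to reject the null hypothesis". Planned enrolment is about 160, 80 per arm.

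**The concern.** The first primary outcome is how far the patient notices smoke, and the plan's reasoning is about closeness to the airway. Within the head and neck that distance still varies, from the nose or lip to the scalp or the neck. Site is known before allocation, since it decides eligibility, so it is a natural factor to use.

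Two things are at stake. If site influences the response, an unadjusted test leaves that variation in the error term. And the arms can differ by chance in their share of near-airway tumours, which would shift the estimate in this particular trial. In most trials either could be dealt with later from the patient record. Here a form without a site code allows neither adjustment for site nor a check of balance among respondents, so the decision has to be made before enrolment.

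**Working it through.** **1. The plan's own figure.** The required size of 140 to 150 cannot be reproduced: the plan says only "Results of a completed pilot study were used to determine a sample size" and shows no effect, response distribution or sidedness. Reading it as a total and the test as two-sided, the standardised difference it implies at 90% power is d = (1.960 + 1.282) × √(4/N).

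- N = 140: d = 0.548
- N = 150: d = 0.529

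This back-solves the plan's number and does not check it. At 160 patients, power is Φ(d × √(160/4) − 1.960): 93.4% if d was sized for 140, and 91.7% if sized for 150.

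**2. Chance imbalance, 80 per arm.** Assumption: a share p of tumours is near the nose or mouth. The standard deviation of the between-arm difference is √(2p(1−p)/80).

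| p | SD (points) | P(gap ≥ 10 points) | P(gap ≥ 15 points) |
|---|---|---|---|
| 0.3 | 7.2 | 19.5% | 4.7% |
| 0.5 | 7.9 | 23.6% | 6.9% |

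These are exact, with two independent binomial counts. If instead a fixed pool of 160 patients is split 80:80 (hypergeometric), a gap of 10 points or more has probability 22.7% to 26.8%.

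Size of the resulting shift: a 10-point gap at a site log odds ratio of 1.0 moves the comparison by about 0.10 × 1.0 = 0.1. The treatment log odds ratio needed for 90% power is about 1.0, so the shift is about a tenth of it.

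**3. Power.** Assumptions: five response levels, N = 146, half the tumours near the airway, and a treatment effect set to give about 90% power unadjusted. The comparison is simple randomisation with the unadjusted trend test against stratified allocation with the site-stratified test.

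| Site log OR | Site acts equally in both arms | Gain | Site acts only in the control arm | Gain |
|---|---|---|---|---|
| 0.5 | 90.2% → 90.5% | 0.3 | 90.1% → 90.1% | 0.0 |
| 1.0 | 89.4% → 91.7% | 2.3 | 89.6% → 89.3% | −0.3 |
| 1.5 | 89.1% → 93.9% | 4.8 | 89.1% → 90.1% | 1.0 |
| 2.0 | 90.2% → 95.8% | 5.6 | 90.5% → 92.3% | 1.8 |

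There were 6,000 runs per case on the left and 5,000 on the right. The simulation error of one power figure is about √(0.9 × 0.1/5000) = 0.4 points, so differences of about a point or less are not distinguishable from zero.

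**4. Hand check of the equal-effect column.** On the logistic scale, half the tumours near the airway and a site log odds ratio b give R² = 0.25b²/(0.25b² + 3.29). Adjusted power is about Φ(3.242/√(1−R²) − 1.960).

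- b = 0.5: R² = 0.019, power 90.5%
- b = 1.0: R² = 0.071, power 92.0%
- b = 1.5: R² = 0.146, power 93.9%
- b = 2.0: R² = 0.233, power 95.9%

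These agree with the simulation.

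**5. Where the gain comes from, and validity.** A second simulation used simple randomisation throughout and changed only the test (N = 150, 40% near-airway, equal site effect in both arms, 10,000 runs per case).

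- R² = 0: 89.3% unadjusted, 89.0% stratified
- R² = 0.06: 89.4% and 90.6%
- R² = 0.19: 88.5% and 93.4%
- R² = 0.35: 86.3% and 96.3%

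The last case lies beyond the range in step 4. The treatment effect was fixed on the underlying scale in these runs and not re-set to 90%, so the lower unadjusted figures are not a shortfall against the plan. The gain appears without stratified allocation, so it comes from the analysis. The unadjusted test kept its type I error at 0.049 to 0.051 in every case.

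**The case against.** A reader might go further and infer any of the following. The documents support none of them.

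- **That site is the main driver of smoke perception.** The Abstract treats the whole head and neck as close to the airway, compares no sites within it and ranks no factors. Eligibility has already removed the widest contrast.
- **That power is lost against the plan.** The unadjusted test holds its level, and the power claim rests on an unreported pilot. If that pilot had mixed sites, its variability would already include site; this cannot be confirmed. Planned enrolment of 160 also exceeds the stated need of 140 to 150.
- **That a site imbalance confounds the result.** Chance imbalance under randomisation is already allowed for in the test's error rate. It can distort one trial's estimate, but it is not a bias of the design.

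The strongest objection concerns the gain itself. If evacuation removes most of the smoke, distance from the airway should matter mainly in the control arm, and the benefit then falls to 0 to 2 points. Reaching about 96% power needs a site odds ratio of e² = 7.4 that persists undiminished under evacuation. Other covariates, such as extent of cautery, could be proposed too, and the proximity argument says little about the third outcome, perceived value.

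All of this stands, and it makes the point minor. It does not remove it: the stratified test costs essentially no power where site does not matter, and the anonymous form rules out a later remedy.

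**Conclusion.** This is a minor, inexpensive improvement and not an error in the plan. Tumour site is a plausible prognostic factor under the plan's own proximity rationale, is unused in allocation and analysis, and cannot be recovered from the forms as described. The efficiency forgone is unknown. It is about 2 to 6 power points at site log odds ratios of 1.0 to 2.0 acting equally in both arms, about 0 to 2 points if site acts mainly in the control arm, and nil if site is weak. A chance imbalance of 10 points or more is expected in roughly 20% to 24% of trials.

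The site effect, the 30% to 50% near-airway share, the five response levels and the two-sided test are assumptions; the documents give none of them.

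**What to change.** Before enrolment:

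1. Print two codes on the anonymous form: the arm, and site in two levels (central face around the nose and mouth, or other head and neck). The two-arm comparison needs the arm code in any case. Neither code identifies a patient.
2. In section 7.c.ii, prespecify one of these as the analysis: the site-stratified trend test (Cochran-Mantel-Haenszel mean-score test), or a proportional-odds model with arm and site, reporting an odds ratio and 95% confidence interval.
3. Optionally, stratify the allocation list by the same site code. This limits imbalance but adds little power beyond step 2, and stratifying without analysing by stratum would not recover the power.

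The cost is one extra non-identifying code on the form, one line of analysis text and, if allocation is stratified, two lists in place of one. Staff must classify site before allocation. No extra patients or visits are needed.
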